9. COMPLIANCE

For patients using Healsea® Children, compliance will be calculated according to the following formula and analysed on the FAS:

$$\text{Compliance (\%)} = \text{Real number of uses} \times 100 / 20$$

With:

- Real number of uses = total number of uses of the treatment from D1 to D10

The number of uses at each day is computed as follows:

- If the patient answered “No” to the question “Did patient use Healsea today?” or “Yes” to the question “Have you not taken Healsea Children today?” then 0;
- If the patient answered “Yes” to the question “Did patient use Healsea today?” then:
 - o If the patient answered “Yes” to the question “Did patient use Healsea once a day?” then 1;
 - o If the patient answered “Yes” to the question “Did patient use Healsea more than twice a day?” then 3;
 - o If he/she did not answer “Yes” neither to the question “Did patient use Healsea once a day?” nor to the question “Did patient use Healsea more than twice a day?” nor to the question “Have you not taken Healsea Children today?” then 2.

Compliance will be described only on Healsea® Children arm.

10. EFFICACY

10.1. Analysis of the primary efficacy criterion

The primary objective will be analysed by performing a t-test (or a Wilcoxon test if the normality assumption is not acceptable) between the means AUC of WURSS-K score during first ten days of symptoms in each group.

The answers of the fourteen first items of the WURSS-K questionnaire are scored **from 0 to 3** (0: negative answer; from 1 to 3: positive answer with an increasing severity level). See the daily symptom report in appendix (§13.3).

The total WURSS-K score at each time point is the sum of the scores of the fourteen first items of the WURSS-K questionnaire:

$$\text{At each time point } t: \text{WURSS}_{\text{tot}}(t) = \sum_{j \in \{1, \dots, 14\}} \text{WURSS}_j(t)$$

AUC of WURSS-K score will be computed by the method described in §6.4.6.

Subjects will be analysed on the Full Analysis Set and the Per-Protocol Set.

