Duration of	Duration of inclusion period: 3 months			
investigation:	Duration of patient's participation: 30 days			
_	Total study duration: 4 months			
Study Start Date:	September 2021			
Statistical Analysis:	The cohort is described: continuous variables will be summarized using the			
,	mean, standard deviation, median, minimum, maximum and quartiles,			
	categorical variables will be summarized using frequency counts and			
	percentages.			
	Two groups (called treatment groups for a sake of simplicity) will be extracted			
	from the cohort according to the treatment chosen by the patient and a			
	description of each group will be performed.			
	accomption of each group will be performed.			
	Details of the statistical analyses, methods and data conventions will be			
	described in the SAP.			
	All statistical tests will be 2-sided and performed using a 0.05 significance level.			
	The selection of variables in multivariate analyses will be performed using a 0.2			
	significance level and a stepwise method. Whole the multivariate analyses			
	specified below involve the treatment and, in order to adjust for confounding,			
	all the potential confounding factors as explanatory variables.			
	The impact of the treatment chosen on the primary endpoint will be analysed			
	by means of a multivariate regression model with the AUC of the WURSS-K			
	during first 10 days of symptoms as dependent variable.			
	The impact of the treatment chosen on the cold symptoms' duration will be			
	analysed by means of a Cox model.			
	The impact of the treatment chosen on the risk to develop respiratory			
	complication requiring antibiotic prescription during a 20-day follow-up period			
	will be analyzed by a multivariate logistic model.			
	The impact of the treatment chosen on the intake of conventional common			
	cold medication (antibiotics, antipyretics, mucolytics, decongestants,			
	antitussives, systemic and topical corticosteroids) will be analyzed by			
	multivariate Poisson regressions for the numbers of days and a multivariate			
	logistic regression for the frequency.			
	logistic regression for the frequency.			

Version: 2.0; 08 Sep 2021 Page **18** of **61**

The impact of the treatment chosen on the number of family members in close contact developing common cold symptoms after the patient all over the study period will be analyzed by means of a multivariate Poisson regression.

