8.1.2 Measures to be taken to minimize or avoid bias

Not applicable.

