8.2 Investigational device and comparator

The investigational device which is Healsea® Children. This is a CE marked Medical Device. Patients/parents will be allowed to use or not the investigational nasal spray. If they choose nasal symptoms to be treated with Healsea® Children, they will start the nasal spray treatment following

Page **31** of **61** Version: 2.0; 08 Sep 2021

their inclusion visit (Visit 1). Healsea® Children will be used on the top of conventional therapies for common cold and administered with the help of an adult, spraying one puff (1-2 sec) twice a day in each nostril for 10 days.

No comparator is used in this study. Patient/parents who prefer not to use Healsea® Children will use conventional therapies for common cold only. **However, use of nasal irrigation will not be authorized for these patients.**

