5. DEFINITION OF THE ANALYSIS SETS

Screened subjects: all subjects who signed an informed consent.

Included subjects: all screened subjects who participated in the study.

Full Analysis Set (FAS): all included subjects who used the investigational medical device at least once.

Per-Protocol (PP) Set: Efficacy population based on the FAS without patients with major protocol deviations.

Safety and Efficacy analyses will be performed on the FAS.

The analyses of the primary and one secondary (modelling of AUC on total WURSS by multivariate ANCOVA) efficacy criteria will also be performed on the PP Set.

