6.3. Statistical/Analytical issues

6.3.1. Significance level

All statistical analyses will be performed at the 0.05 global significance level (type I error rate), using two-sided tests.

The statistical results are conclusive for the primary efficacy criterion.

All the other statistical results have to be considered within a descriptive perspective and not as inferential issues. No adjustment for Type I error is done. P-values of statistical tests will be provided for information only.

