10.2. Analysis of the secondary efficacy criteria

The analysis of the secondary endpoints will involve multivariate analysis.

The selection of variables in multivariate analysis will be performed using a 0.20 significance level and a stepwise method. Whole the multivariate analyses specified below involve the treatment and, in order to adjust for confounding, all the potential confounding factors as explanatory variables:

- Temperature at baseline (°C);
- Symptoms' scores at baseline.

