10.2.1. Modelling of AUC on total WURSS by multivariate ANCOVA

The analysis of the impact of the treatment chosen on the primary endpoint will be enriched by means of a multivariate ANCOVA model with the AUC of the WURSS-K during first ten days of symptoms as dependent variable. Subjects will be analysed on the Full Analysis Set and the Per-Protocol Set.

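### Families choose the group, yet the only conclusive test of the primary endpoint is unadjusted, and the adjusted model of the same AUC is merely descriptive

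*SAP*

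**What the plan says.** **Allocation.** There is no randomisation. Protocol 8.2 says "Patients/parents will be allowed to use or not the investigational nasal spray", and Protocol 9.1 forms the two analysis groups from that choice. Under the heading "Measures to be taken to minimize or avoid bias" (Protocol 8.1.2) the entry is that this does not apply. Protocol 8.3.14 sees no foreseeable factor that could compromise the outcome.

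**Primary analysis.** Protocol 9.3 and SAP 10.1 agree: "The primary objective will be analysed by performing a t-test", or a Wilcoxon test if normality is not acceptable, on the 10-day WURSS-K AUC. No covariate enters. The synopsis differs. It analyses the effect of the chosen treatment on the primary endpoint "by means of a multivariate regression model with the AUC of the WURSS-K" as dependent variable, adjusted for confounding (no covariates are named), and mentions no t-test.

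**Status of the adjusted model.** SAP 5 counts it as "one secondary (modelling of AUC on total WURSS by multivariate ANCOVA) efficacy criteria". SAP 10.2.1 says the primary analysis "will be enriched by means of a multivariate ANCOVA model". SAP 6.3.1 calls results conclusive for the primary criterion only and adds: "All the other statistical results have to be considered within a descriptive perspective and not as inferential issues".

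**Covariates.** SAP 10.2 has the multivariate models include treatment and, "in order to adjust for confounding, all the potential confounding factors as explanatory variables", with stepwise selection at 0.20. The list that follows holds only baseline temperature and baseline symptom scores.

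**The concern.** The hypothesis in Protocol 7.1 is comparative: the spray plus conventional therapy works better than conventional therapy alone. When families choose, the choice may follow how ill the child is, which other medicines are in use, or the centre. An unadjusted comparison then estimates the device effect plus the difference between the kinds of children who end up in each group. Its 5% error rate no longer refers to a device effect.

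The plan recognises this, because it adjusts the secondary endpoint models for confounding. The one test that carries the conclusion is left without adjustment. Bias can go either way. If milder cases choose the spray, an effect may be claimed that is not there. If sicker children choose it, a real benefit may be missed.

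**Working it through.** **1. The plan's own figure.** Inputs from SAP 4 and 6.3.1: 100 per group, standardised difference 0.4, two-sided 5%. The normal approximation needs 99 per group for 80% power. At 100 per group, power is 80.7% (normal) or 80.4% (exact noncentral t). The figure reproduces, on the premise that the groups differ only by treatment.

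**2. Adding a baseline imbalance.** Let r be the within-group correlation between a baseline factor and AUC, and D the between-group difference in that factor, in SDs. Neither is in the documents, so both are assumptions. With a within-group AUC SD of 1:

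- bias b = r × D
- SE = √(2/100) = 0.1414
- chance of a significant result when the expected difference is δ: Φ(δ/SE − 1.96) + Φ(−δ/SE − 1.96)

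The false-positive rate uses δ = b. Power for a true 0.4 SD benefit with the sicker children in the device group uses δ = 0.4 − b. Example: r = 0.5 and D = 0.3 give b = 0.15 and b/SE = 1.06, so the rate is Φ(−0.90) + Φ(−3.02) ≈ 18.6%.

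| r | D | b | False positives, unadjusted | Power, unadjusted, device group sicker |
|---|---|---|---|---|
| 0.3 | 0.1 | 0.03 | 5.5% | 74.4% |
| 0.5 | 0.2 | 0.10 | 10.9% | 56.4% |
| 0.5 | 0.3 | 0.15 | 18.6% | 42.4% |
| 0.5 | 0.4 | 0.20 | 29.3% | 29.3% |
| 0.5 | 0.5 | 0.25 | 42.4% | 18.6% |
| 0.7 | 0.4 | 0.28 | 50.8% | 13.6% |

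The exact t calculation gives 18.4% for b = 0.15 and 42.1% for b = 0.25.

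**3. Unadjusted and adjusted analysis by simulation** (6,000 runs per scenario; ANCOVA with treatment, the imbalanced covariate and five unrelated ones; r = 0.5):

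| D | Truth | t-test | Wilcoxon | ANCOVA |
|---|---|---|---|---|
| 0.3 | no effect | 19.3% | 18.5% | 5.1% |
| 0.5 | no effect | 42.6% | 40.6% | 4.7% |
| 0.3 | benefit 0.4, device group sicker | 42.5% | – | 88.1% |
| 0.5 | benefit 0.4, device group sicker | 18.9% | – | 87.0% |

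Switching to the Wilcoxon test gives almost no protection.

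**4. What adjustment cannot do.** Take a confounder that is not recorded, with r = 0.3 and D = 0.5, so again b = 0.15. Simulation gives 18.8% false positives for the t-test and 22.4% for ANCOVA. ANCOVA is slightly worse because a prognostic covariate shrinks the SE while the bias stays. If that covariate correlates 0.5 with AUC, SE = √(0.75 × 0.02) = 0.122, and Φ(0.15/0.122 − 1.96) ≈ 23%.

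**The case against.** Several counter-arguments have weight.

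- **No sentence in the SAP says which analysis wins if they disagree.** True. But SAP 5 makes the ANCOVA secondary, and SAP 6.3.1 makes everything outside the primary criterion descriptive. That the unadjusted result decides follows from those two sections together.
- **The adjusted answer is already planned.** The ANCOVA is pre-specified on both analysis sets, its table shell shows an adjusted difference with a 95% CI, and SAP 8.4 tests baseline temperature and symptom scores between groups. In a simulation with one confounder on the candidate list, selection at 0.20 kept it in at least 99.9% of runs, with false positives of 4.5–5.0%. So for temperature and symptom scores the report would show much of what is needed. It would still carry no weight in the conclusion, and the SAP 8.4 tests trigger no action. Age, sex and baseline medication are not candidates at all.
- **The imbalances are assumed and could be small.** This stands. Eligibility limits age, symptom duration, total symptom score and recent medication, and the mildest case above gives only 5.5%.
- **Adjustment does not restore 5% in general.** This stands too. Unrecorded family preference, and open-label diary scoring by child or parent, remain. That is a reason to state the limit, not to leave recorded confounders out.
- **Changing the conclusive test late carries its own risk.** SAP 12 shows that diary answers had already been examined. This bears on how the change is documented.

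**Conclusion.** The plan is wrong as written on this point. The synopsis and Protocol 9.3 contradict each other, the SAP follows 9.3, and SAP 12 does not reconcile them. As a result, the study's single confirmatory conclusion rests on a comparison of self-selected groups that ignores confounders the study records.

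The direction and size of the actual bias cannot be derived from the documents. Under the assumptions shown, false positives range from 5.5% to about 51%, and power for the design effect falls from 80% to between 74% and 14% when the sicker children choose the spray. A bias of only 0.1 SD of AUC doubles the error rate to 10.9%. Adjustment returns the error to about 5% only for confounders that are measured and kept in the model. The sample size arithmetic itself is not in dispute.

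**What to change.** Make the SAP 10.2.1 ANCOVA the primary, conclusive analysis. Align Protocol 9.3 and SAP 5, 6.3.1 and 10.1 with the synopsis, and keep the t-test or Wilcoxon as unadjusted support.

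Replace stepwise selection in this model with a fixed set that is already collected: baseline temperature, baseline total symptom score, age, sex, and baseline allergy or topical corticosteroid medication. The total score keeps the model small; the eight single scores can go into a supporting model. State in both documents that unmeasured confounding remains.

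Optional additions:

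- **Enrolment date.** Each group closes separately at 100 (Protocol 7.4). With constant arrivals, if 60% or 75% choose one option, that group closes after 100/0.60 = 167 or 100/0.75 = 133 children, and about 33 or 67 of the other group's 100 enrol later. A date term then extrapolates. It also costs power. The imbalance in date is D ≈ 0.68 or 1.55, the variance of the treatment effect grows by 1 + D²/4 = 1.12 or 1.60, and power for 0.4 SD falls from 81% to about 76% or 61% if date is unrelated to AUC. It fits better in a sensitivity analysis.
- **Children enrolled while both groups were open.** This comparison avoids the extrapolation, but with 100 against 67 or 33 children its unadjusted power is 71% or 51%.
- **Centre.** Use a random effect or a sensitivity analysis. Forced fixed effects for 15 centres give power 0.77, 0.69, 0.53 or 0.44 as choice clusters more by centre (logit SD 0, 1, 2, 3). The cost of a random effect was not computed.

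**Cost of the main change.** It needs protocol and SAP wording and no new data. Even six covariates, balanced and unrelated to AUC, give 79% power against 80%; if one correlates 0.5 with AUC, power is 89%. Because diary answers had been seen, the amendment must record that it was made without reference to outcome data by group.

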10.2. Analysis of the secondary efficacy criteria

The analysis of the secondary endpoints will involve multivariate analysis.

The selection of variables in multivariate analysis will be performed using a 0.20 significance level and a stepwise method. Whole the multivariate analyses specified below involve the treatment and, in order to adjust for confounding, all the potential confounding factors as explanatory variables:

- Temperature at baseline (°C);
- Symptoms' scores at baseline.

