8.3.2.3 Subject replacement

It is not anticipated to replace withdrawal patients.

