9.4 Secondary endpoints

The analysis of the secondary endpoints will involve multivariate analysis.

The selection of variables in multivariate analysis will be performed using a 0.2 significance level and a stepwise method. Whole the multivariate analyses specified below involve the treatment and, in order to adjust for confounding, all the potential confounding factors as explanatory variables.

The analysis of the impact of the treatment chosen on the primary endpoint will be enriched by means of a multivariate regression model with the AUC of the WURSS-K during first 10 days of symptoms as dependent variable.

The impact of the treatment chosen on the cold symptoms' duration will be analysed by means of a Cox model.

The impact of the treatment chosen on the risk to develop respiratory complication requiring antibiotic prescription during a 20-day follow-up period will be analyzed by a multivariate logistic model.

The impact of the treatment chosen on the intake of conventional common cold medication (antibiotics, antipyretics, mucolytics, decongestants, antitussives, systemic and topical corticosteroids) will be analyzed by multivariate Poisson regressions for the numbers of days and a multivariate logistic regression for the frequency.

The impact of the treatment chosen on the number of family members in close contact developing common cold symptoms after the patient all over the study period will be analyzed by means of a multivariate Poisson regression.

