4. SAMPLE SIZE

An arbitrary cohort of 200 children has been chosen. A cohort of 100-exposed and 100-not exposed patients is anticipated to allow to demonstrate the interest of using Healsea® Children in the allergic paediatric population.

Indeed, 100 patients by arms are enough to detect a Cohen's effect size of 0.4 with a power of 80% and a type I error of 5%. Cohen's effect size is defined as the standardized difference between AUC in groups. Following Cohen's methodology, 0.4 is an intermediate size between a small effect (0.2) and a medium effect (0.5) and is coherent with the expected result.

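### The plan selects covariates stepwise at p<0.20 yet also requires all potential confounders in the model; the adjusted models need one fixed, short covariate set

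*SAP*

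**What the plan says.** SAP 10.2 governs the secondary efficacy models. It first states "The selection of variables in multivariate analysis will be performed using a 0.20 significance level and a stepwise method". The next sentence has the analyses involve the treatment and, "in order to adjust for confounding, all the potential confounding factors as explanatory variables". Two items follow: baseline temperature and the baseline symptom scores. It does not say whether the eight item scores, their total, or both are meant.

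Protocol 9.4 repeats the rule ("The selection of variables in multivariate analysis will be performed using a 0.2 significance level and a stepwise method") and the sentence after it, without naming the confounders. The synopsis, under Statistical Analysis, also selects at a 0.2 "significance level and a stepwise method" beside the same requirement.

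The setting is as follows:

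- **Treatment choice.** The family chooses the treatment at Visit 1 (Protocol 8.2 and 8.3.11; SAP 3). Protocol 8.1.2 lists no measures against bias.
- **Primary analysis.** SAP 10.1 and Protocol 9.3 use a t-test or Wilcoxon test without covariates. The synopsis instead names the multivariate regression for the primary endpoint and mentions no t-test.
- **Status of the adjusted models.** SAP 6.3.1 makes only the primary criterion conclusive. Other results are descriptive and their p-values informative only.
- **Mock tables (SAP 13.2).** The ANCOVA, logistic and Poisson shells print a treatment row and leave the other terms open. The Cox shell has one hazard ratio and no covariate rows.

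**The concern.** Both sentences cannot govern the final model. Either every listed confounder stays in, or a p-value decides. Neither document says which prevails or which terms are forced.

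The choice matters because treatment is self-selected. Selection on outcome p-values looks for predictors, whereas confounding depends on the product of group imbalance and outcome effect. Several weak predictors that are imbalanced in the same direction can each fail the 0.20 threshold and together leave bias. The final model's standard error is then computed as if that model had been fixed in advance. Different endpoints, or the FAS and PP fits of the same ANCOVA, can end up adjusted for different variables, so their estimates are not comparable.

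**Working it through.** **1. The plan's own figure.** SAP 4 gives 100 per group, a standardised difference of 0.4, 80% power and 5% type I error. n per group = 2(1.960 + 0.842)²/0.4² = 98.1, so 99. With 100 per group the power is Φ(0.4√50 − 1.960) = Φ(0.868) = 80.7%. The figure reproduces, and covariate selection does not affect it. The reference level for what follows is SAP 6.3.1: "All statistical analyses will be performed at the 0.05 global significance level (type I error rate), using two-sided tests".

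**2. How many models are exposed.** SAP 10.2 and the table list give 2 ANCOVA fits (FAS, PP), 6 Cox, 1 complication logistic, 16 medication models (8 tables × 2) and 1 Poisson model for family contacts. That is 26, or 20 if Cox is unadjusted.

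**3. Chance that one confounder is dropped.** With n = 200, partial correlation r with the outcome and threshold z = 1.2816, P(drop) = Φ(1.2816 − ζ) − Φ(−1.2816 − ζ), where ζ = atanh(r)√195. For r = 0.10, ζ = 1.401 and P = 0.449.

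| r | 0.05 | 0.10 | 0.15 | 0.20 | 0.30 |
|---|---|---|---|---|---|
| P(dropped) | 70% | 45% | 20% | 6% | 0.1% |

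**4. Simulation.** The documents give no imbalances, effects or correlations, so these are assumptions. There are 100 children per group and nine candidates (temperature plus the eight symptoms in Protocol 8.3.1.1, criterion 5). Each has an outcome effect of 0.1 SD and an imbalance of 0.3 or 0.5 SD, all in one direction. Pairwise correlation is 0.3 or 0, the true treatment effect is zero, treatment is forced in, and entry and removal are both at 0.20. Each setting has 2,500 runs.

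As a check, unadjusted bias should be 9 × 0.1 × 0.3 = 0.27 or 9 × 0.1 × 0.5 = 0.45, and the runs agree.

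| Imbalance / correlation | Model | Bias (SD) | Mean SE ÷ true SD | Coverage | Type I error |
|---|---|---|---|---|---|
| 0.3 / 0.3 | unadjusted | +0.267 | 1.007 | 62.6% | 37.4% |
| | nine fixed | −0.003 | 1.006 | 94.9% | 5.1% |
| | stepwise | +0.009 | 0.975 | 94.1% | 5.9% |
| 0.5 / 0.3 | unadjusted | +0.452 | 1.003 | 20.9% | 79.1% |
| | nine fixed | +0.003 | 1.001 | 95.6% | 4.4% |
| | stepwise | +0.023 | 0.958 | 94.2% | 5.8% |
| 0.5 / 0 | unadjusted | +0.447 | 0.996 | 14.6% | 85.4% |
| | nine fixed | −0.005 | 0.987 | 94.7% | 5.3% |
| | stepwise | +0.077 | 0.821 | 86.7% | 13.3% |

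Stepwise dropped 4.1 of the nine on average in each setting. The simulation error of a 5% rate is √(0.05 × 0.95/2500) = 0.4 points. A separate simulation of the same kind gave stepwise type I error of 5.5–6.3% with correlated covariates and 13.7% with uncorrelated covariates and 0.5 SD imbalance, against 5.0–6.2% for the full model.

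**5. Sparse logistic models.** The documents give no event rates. With n = 200 and nine covariates of assumed weak effect plus treatment forced in, 23% of fits failed at about 5 events. At about 12 events the mean SE was 0.76 against a true SD of 0.84 (ratio 0.90). At about 24 events there was no problem. A fixed set therefore has to be short.

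**The case against.** The strongest reply has four parts.

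- **Descriptive status.** SAP 6.3.1 ties the declared conclusion to an unadjusted test that stepwise selection never touches. This stands, and it limits the severity. The adjusted estimates and intervals will still be reported, and a descriptive interval should have its stated coverage.
- **Small effect with correlated scores.** The excess over the fixed model is at most about one point and near simulation error. This also stands for that setting. Symptoms of one cold tend to move together. However, inclusion criterion 5 caps their sum at 9 of a possible 8 × 3 = 24, which weakens correlation between items, so the uncorrelated case cannot be dismissed.
- **Most confounding is removed anyway.** Stepwise leaves 0.009/0.267 = 3%, 0.023/0.452 = 5% and 0.077/0.447 = 17% of the unadjusted bias. Strong confounders are nearly always kept. True, but a fixed set leaves essentially none in the same settings.
- **Forcing all nine can harm sparse models.** This stands, and it shapes the fix.

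Three stronger readings are tempting but not supported. A reader might infer that the treatment term itself can be removed. Forcing is not stated, but the adjacent sentence has the analyses involve the treatment, and every model shell reports a treatment effect. A reader might also infer that weak outcome predictors are precisely the variables that confound. Bias is roughly imbalance times outcome effect, so each weak predictor confounds only weakly. Finally, Table 14.1.2.4 shows both the items and their total, but it is a baseline description and does not establish that both are model candidates.

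**Conclusion.** The contradiction is real and appears in SAP 10.2, Protocol 9.4 and the synopsis. If the stepwise sentence is followed, it weakens the only planned control of confounding in a study where families choose the treatment.

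The size depends on assumptions. About 4 of 9 weak confounders are lost. Type I error is about 5.5–6.3% with correlated covariates and 13–14% with uncorrelated covariates and 0.5 SD imbalance, against 4.4–6.2% with the nine fixed. The upper figure requires all nine confounders to act in one direction. These results are for the linear model, and the fixed comparator was the nine-covariate model, not the shorter set proposed below.

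The SAP's conclusive primary test is unaffected. Whether the rule reaches the Cox models is unclear: SAP 10.2 groups them with the multivariate analyses, but SAP 10.2.2 does not call them multivariate and their shell shows no covariates. This should be corrected, but it does not overturn a planned conclusion.

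**What to change.** Delete the stepwise sentence in SAP 10.2, Protocol 9.4 and the synopsis, or keep stepwise only as a labelled sensitivity analysis. Replace it with wording such as: *Every adjusted model, including the Cox models, contains treatment, baseline temperature and the total baseline symptom score. No term is added or removed on the basis of the data.* Use the total alone, not the eight items plus the total. Add the covariate rows to the Cox shell and record the change in SAP 12 before any adjusted model is run.

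The cost is wording and simpler programming, with no change in sample size. Intervals become slightly wider. With all nine covariates fixed, the mean SE rose from 0.146 to 0.149 (2%), from 0.152 to 0.156 (3%) and from 0.163 to 0.181 (11%); in the last case the stepwise SE was well below the true SD. The short set has three terms.

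Two limits remain. With very few events in a logistic model, even three terms may need a penalised fit or a descriptive table only. The total also cannot fully adjust for an imbalance confined to one symptom; an ANCOVA sensitivity analysis with the eight items in place of the total would show whether this matters.
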